**PLEASE COMPLETE AND EMAIL COPY TO HCRN**

## SYNOPSIS

TITLE	A Randomized, Phase II Trial to Evaluate the Efficacy of Supportive Therapy with Ginseng for Patients on Treatment with Regorafenib
SHORT TITLE	Efficacy of Ginseng for Patients on Regorafenib
PHASE	Phase II
OBJECTIVES	
Primary Objective: Assess fatigue with the Multidimensional Fatigue Symptom Inventory-Short Form (MFSI-SF) and Patient-Reported Outcomes Measurement Information System (PROMIS) form for each group (Regorafenib + No Ginseng vs. Regorafenib + Ginseng) to determine if 2000 mg of American Ginseng for 8 weeks has an impact on the fatigue score
 
Secondary Objectives:
 
 
1) Assess the effect of Ginseng on adherence to Regorafenib for CRC subjects with good performance status
 
2) Assess the toxicities of the combination of Regorafenib and Ginseng for CRC subjects with good performance status
 
3) Assess the retention of subjects to the combination of Regorafenib and Ginseng for CRC subjects with good performance status
 
4) Evaluate response rate and overall survival
 

STUDY DESIGN	Randomized
ESTIMATED NUMBER OF SUBJECTS	90: 60 randomized to regorafenib + ginseng and 30 to regorafenib + no ginseng
KEY ELIGIBILITY CRITERIA	
Inclusion criteria:
 
 
1. Subjects must be able to understand and be willing to sign the written informed consent and HIPAA authorization for release of personal health information. A signed informed consent form must be appropriately obtained prior to the conduct of any trial-specific procedure.
 
 
NOTE: HIPAA authorization may be included in the informed consent or obtained separately.
 
 
2. Age <math>\geq</math> 18 years at the time of consent.
 
3. Life expectancy of at least 12 weeks (3 months).
 
4. ECOG Performance Status of 0 or 1 within 28 days prior to registration.
 
5. Histological or cytologically confirmed stage IV adenocarcinoma of the colon.
 
6. Adequate bone marrow, liver and renal function as assessed by the following laboratory values obtained within 7 days prior to registration for protocol therapy.           
 
a. Absolute neutrophil count (ANC) count <math>> 1,500/\text{mm}^3</math>
 
b. Hemoglobin (Hgb) <math>> 9\text{g/dL}</math>
 
c. Platelet count <math>> 100,000/\text{mm}^3</math>
 
d. Total bilirubin <math>\leq 1.5 \times</math> the upper limit of normal (ULN).
 
e. Alanine aminotransferase (ALT) and aspartate amino-transferase (AST) <math>\leq 2.5 \times</math> ULN (<math>\leq 5 \times</math> ULN for subjects with liver involvement of their cancer)
 
f. Alkaline phosphatase limit <math>\leq 2.5 \times</math> ULN (<math>\leq 5 \times</math> ULN for subjects with liver involvement of their cancer)
 
g. Serum creatinine <math>\leq 1.5 \times</math> the ULN
 
 
 

h. International normalized ratio (INR)/ Partial thromboplastin time (PTT) < 1.5 × ULN. (Subjects who are prophylactically treated with an agent such as warfarin or heparin will be allowed to participate if no prior evidence of underlying abnormality in coagulation parameters exists. Close monitoring of at least weekly evaluations will be performed until INR/PTT is stable based on a measurement that is pre-dose as defined by the local standard of care.)

7. Women of childbearing potential must have a negative serum pregnancy test performed within 7 days prior to the start of study drug. Post-menopausal women (defined as no menses for at least 1 year) and surgically sterilized women are not required to undergo a pregnancy test. The definition of adequate contraception will be based on the judgment of the site investigator.

8. Subjects (men and women) of childbearing potential must agree to use adequate contraception beginning at the signing of the ICF until at least 2 months after the last dose of study drug. The definition of adequate contraception will be based on the judgment of the treating physician or a designated associate. Examples of adequate contraception may include but are not limited to a combination of any two of the following:

- Use of oral, injected or implanted hormonal methods of contraception
- Placement of an intrauterine device (IUD) or intrauterine system (IUS)
- Barrier methods of contraception: condom or occlusive cap (diaphragm or cervical/vault caps) with spermicidal foam/gel/film/cream/vaginal suppository
- Total abstinence
- Male/female sterilization

9. All subjects must have radiographically assessable disease per RECIST v1.1 obtained by imaging within 28 days prior to registration.

10. Must be able to swallow and retain oral medication.

11. Subject must be deemed a suitable candidate for regorafenib as per their treating physician

#### **Exclusion Criteria**

1. Subject should not be receiving any agent for fatigue including steroids or megace.  
**NOTE:** Subjects who have a contrast-induced allergy are allowed to receive steroids for their scans.
2. Radiotherapy within 2 weeks prior to randomization. Subjects must have recovered from all therapy-related toxicities.
3. Prior treatment with regorafenib.
4. Previous assignment to treatment during this study. Subjects permanently withdrawn from study participation will not be allowed to re-enter study.
5. Congestive heart failure > New York Heart Association (NYHA) class 2.
  - i. Unstable angina (angina symptoms at rest), new-onset angina (begun within the last 3 months). Myocardial infarction less than 6 months before start of study medication.
  - ii. Cardiac arrhythmias requiring anti-arrhythmic therapy (beta blockers or digoxin are permitted).
  - iii. Uncontrolled hypertension (systolic blood pressure > 150 mmHg or diastolic pressure > 90 mmHg despite optimal medical management).

	
 
6. Evidence or history of bleeding diathesis or coagulopathy.
 
7. Any hemorrhage or bleeding event <math>\geq</math> NCI CTCAE Grade 3 within 4 weeks prior to start of study medication.
 
8. Subjects with thrombotic, embolic, venous, or arterial events, such as cerebrovascular accident (including transient ischemic attacks) deep vein thrombosis or pulmonary embolism within 6 months of start of study treatment or within 6 months of informed consent.
 
9. Previous or concurrent cancer that is distinct in primary site or histology from colorectal cancer within 3 years prior to randomization EXCEPT for curatively treated cervical cancer in situ, non-melanoma skin cancer and superficial bladder tumors [Ta (Non-invasive tumor), Tis (Carcinoma in situ) and T1 (Tumor invades lamina propria)].
 
10. Subjects with pheochromocytoma.
 
11. Known history of human immunodeficiency virus (HIV) infection or current chronic or active hepatitis B or C infection requiring treatment with antiviral therapy.
 
12. Ongoing infection <math>></math> Grade 2 NCI-CTCAE v4.0.
 
13. Metastatic brain or meningeal tumors (symptomatic or asymptomatic).
 
14. Major surgical procedure or significant traumatic injury within 28 days before start of study medication
 
15. Renal failure requiring hemo- or peritoneal dialysis.
 
16. Dehydration Grade <math>></math> 1 NCI CTCAE v4.0.
 
17. Subjects with seizure disorder requiring medication.
 
18. Persistent proteinuria <math>\geq</math> Grade 3 NCI CTCAE v4.0 (<math>></math> 3.5 g/24 hours, measured by urine protein: creatinine ratio on a random urine sample).
 
19. Interstitial lung disease with ongoing signs and symptoms at the time of informed consent.
 
20. Pleural effusion or ascites that causes respiratory compromise (<math>\geq</math> NCI CTCAE version 4.0 Grade 2 dyspnea).
 
21. History of organ allograft (including corneal transplant).
 
22. Known or suspected allergy or hypersensitivity to any of the study drugs, study drug classes, or excipients of the formulations given during the course of this trial.
 
23. Any malabsorption condition.
 
24. Women who are pregnant or breast-feeding.
 
25. Any condition, which, in the site investigator's opinion, makes the subject unsuitable for trial participation.
 
26. Substance abuse, medical, psychological, or social conditions that may interfere with the subject's participation in the study or evaluation of the study results.
 
27. Treatment with any investigational agent within 28 days prior to registration.
 

STATISTICAL CONSIDERATIONS	
Ninety (90) subjects will be enrolled and randomized using a 2:1 allocation with 60 subjects enrolled in the Regorafenib + Ginseng group and 30 enrolled in the Regorafenib + placebo No Ginseng group. Expected standard deviations for the outcome of interest are 27.0 for the Ginseng group and 26.1 for the no ginseng group. Using a two group Satterthwaite t-test with a 0.050 two-sided significance level, there is 80% power to detect a difference between groups if the change in the No

	Ginseng group is 10 and the change in the Ginseng group is 27 (or greater). A two-sided 95.0% confidence interval for the difference of the two means (change in fatigue score for Ginseng group vs change in fatigue score for no ginseng group) will extend 11.833 from the observed difference in means, assuming that the common standard deviation is 27.0 (conservatively choosing the standard deviation from the Ginseng group since it is larger than the no ginseng standard deviation) when the sample sizes are 60 and 30 respectively (a total sample size of 90) and the confidence interval is based on the large sample z statistic.
ESTIMATED ENROLLMENT PERIOD	12 months
ESTIMATED STUDY DURATION	18 months

## **LIST OF ABBREVIATIONS**

ADL	Activities of Daily Living
AE	Adverse event
ALT	Alanine aminotransferase
Ang	Angiopoietin
aPTT	Activated partial thromboplastin time
AST	Aspartate aminotransferase
BCRP	Breast Cancer Resistance Protein
BID	bis in die , twice daily
BP	Blood pressure
B-Raf	B isoform of Rapidly Accelerated Fibrosarcoma protein
BUN	Blood Urea Nitrogen
CBC	Complete blood count
CCCWFU	Comprehensive Cancer Center of Wake Forest University
CFR	Code of Federal Regulations
c-KIT	Stem Cell Factor Receptor Tyrosine Kinase
CR	Complete Response
C-RAF	C isoform of Rapidly Accelerated Fibrosarcoma protein
CRC	Colorectal cancer
CRF	Cancer-related fatigue
CTCAE	Common Terminology Criteria for Adverse Events
CTEP	Cancer Therapy Evaluation Program
CYP2C19	Cytochrome P450 2C19
CYP2D6	Cytochrome P450 2D6
CYP3A4	Cytochrome P450 3A4
DCE	Dynamic Contrast Enhanced
DMSO	Dimethyl sulfoxide
DSMC	Data and Safety Monitoring Committee
DSMP	Data and Safety Monitoring Plan
ECOG	Eastern Cooperative Oncology Group
eCRF	Electronic case report form
EDC	Electronic data capture
EGFR	Epidermal growth factor receptor
EOT	End of treatment
ERK	Extracellular Signal-regulated Kinases
FACT-F	Functional Assessment of Cancer Therapy: Fatigue
FDA	Food and Drug Administration
FGFR	Fibroblast Growth Factor Receptor
FLT3	FMS-like Tyrosine Kinase 3
GCP	Good Clinical Practice
GMP	Good Manufacturing Practice
HCC	Hepatocellular carcinoma
HCRN	Hoosier Cancer Research Network
HFSR	Hand-foot-skin reaction
Hgb	Hemoglobin
HIPAA	Health Insurance Portability and Accountability Act of 1996

HPA	Hypothalamic-pituitary-adrenal
IB	Investigator's Brochure
IC 50	Half Maximal Inhibitory Concentration
ICF	Informed Consent Form
ICH	International Conference on Harmonisation
IND	Investigational New Drug
IL-1 $\beta$	Interleukin 1 beta
IL-2	Interleukin 2
IL-6	Interleukin 6
IL-8	Interleukin 8
INR	International normalized ratio
IR	Immediate Release
IRB	Institutional Review Board
MAPK	Mitogen Activated Protein Kinase
MEK	MAP Kinase / ERK Kinase 1
MFSI-SF	Multidimensional Fatigue Symptom Inventory-Short Form
mL	Milliliter
NCI	National Cancer Institute
NM	Nanomolar
NYHA	New York Heart Association
PBMC	Peripheral blood mononuclear cell
PD	Progressive Disease
PDGFR- $\beta$	Platelet Derived Growth Factor Receptor-beta
PFS	Progression free survival
po	per oris , oral
PR	Partial Response
PROMIS	Patient Reported Outcomes Measurement Information System
PS	Performance Status
PTT	Partial thromboplastin time
QC	Quality control
QOL	Quality of life
RAF	Rapidly Accelerated Fibrosarcoma
RAS	Rat sarcoma
RCC	Renal Cell Carcinoma
RECIST	Response Evaluation Criteria for Solid Tumors
RET	Rearranged during transfection
rpm	Revolutions per minute
RPMI-1640	Roswell Park Memorial Institute medium 1640
RTK	Receptor Tyrosine Kinase
SAE	Serious Adverse Event
SD	Stable Disease
SPM	Study Procedures Manual
SUSARs	Suspected Unexpected Serious Adverse Reactions
TIE2	Tyrosine kinase with Immunoglobulin and Epidermal Growth Factor (EGF) homology domain 2
TK	Tyrosine Kinase

TK	Tyrosine Kinase
TNF- $\alpha$	Tumor necrosis factor alpha
TPP	Time to Progression
UGT1A1	UDP-glucuronosyltransferase 1-1
UGT1A9	UDP-glucuronosyltransferase 1-9
ULN	Upper limit of normal
VEGF	Vascular Endothelial Growth Factor
VEGFR	Vascular Endothelial Growth Factor Receptor
WBC	White blood cell

**Specific Hypothesis:** Regorafenib is a recently approved active, third line treatment for good performance status patients with CRC. One of the potential treatment-limiting toxicities is fatigue, observed in approximately 50% of the patients. We hypothesize that Ginseng will decrease fatigue and increase adherence to chemotherapy for patients receiving regorafenib for colon cancer. The fatigue level will be evaluated with 2 different scales: MFSI-SF (multidimensional fatigue symptom inventory-short form) and PROMIS (Patient-Reported Outcomes Measurement Information System) Short Form v1.0 – Fatigue 8a [4]. The Patient-Reported Outcomes Measurement Information System (PROMIS) initiative is an example of an effort to develop a standard battery of valid and reliable measures that can be used in symptom management and QOL research [5]. We will use the MFSI-SF tool that was used in the original ginseng study by Barton et.al and compare its results with the PROMIS scale which represents the NCI recommended tool to evaluate symptoms in oncology clinical trials [6].

## 2. STUDY OBJECTIVES AND ENDPOINTS

### 2.1. Primary Objective

Assess the difference in fatigue scores using the Multidimensional Fatigue Symptom Inventory-Short Form (MFSI-SF) and Patient-Reported Outcomes Measurement Information System (PROMIS Short Form v1.0 – Fatigue 8a) for each group (Regorafenib+ No Ginseng vs. Regorafenib + Ginseng) to determine if 2000 mg of American Ginseng for 8 weeks has an impact on the fatigue score.

### 2.2. Secondary Objectives

- 1) Assess the difference in adherence to regorafenib between the two groups. Pill counts will be used to assess adherence. The hypothesis is that Ginseng may increase adherence by decreasing fatigue.
- 2) Assess the difference in toxicities between the two arms.
- 3) Assess the difference in retention between the two arms. Retention is the proportion of subjects who complete the study. Note that they may not completely adhere to the study medication, but as long as they come in for the last measurements, they are considered retained.
- 4) Assess response rate and overall survival

### 2.3 Endpoints

Fatigue score, adherence, toxicity and retention

## 3. ELIGIBILITY CRITERIA

### 3.1. Inclusion Criteria

1. Subjects must be able to understand and be willing to sign the written informed consent and HIPAA authorization for release of personal health information. A signed informed consent form must be appropriately obtained prior to the conduct of any trial-specific procedure.  
**NOTE:** HIPAA authorization may be included in the informed consent or obtained separately.
2. Age  $\geq$  18 years at the time of consent.
3. Life expectancy of at least 12 weeks (3 months) as determined by the treating physician.
4. ECOG Performance Status of 0 or 1 within 28 days prior to registration.
5. Histological or pathologically confirmed stage IV adenocarcinoma of the colon.

6. Adequate bone marrow, liver and renal function as assessed by the following laboratory values obtained within 7 days prior to registration for protocol therapy.
  - Absolute neutrophil count (ANC) count  $> 1,500/\text{mm}^3$
  - Hemoglobin (Hgb)  $> 9\text{g/dL}$
  - Platelet count  $> 100,000/\text{mm}^3$
  - Total bilirubin  $\leq 1.5 \times$  the upper limit of normal (ULN).
  - Alanine aminotransferase (ALT) and aspartate amino-transferase (AST)  $\leq 2.5 \times$  ULN ( $\leq 5 \times$  ULN for subjects with liver involvement of their cancer)
  - Alkaline phosphatase limit  $\leq 2.5 \times$  ULN ( $\leq 5 \times$  ULN for subjects with liver involvement of their cancer)
  - Serum creatinine  $\leq 1.5 \times$  the ULN
  - International normalized ratio (INR)/Partial thromboplastin time (PTT)  $< 1.5 \times$  ULN.  
**NOTE:** Subjects who are prophylactically treated with an agent such as warfarin or heparin will be allowed to participate if no prior evidence of underlying abnormality in coagulation parameters exists. Close monitoring of at least weekly evaluations will be performed until INR/PTT is stable based on a measurement that is pre-dose as defined by the local standard of care. Warfarin dose should not exceed 1 mg
7. Women of childbearing potential must have a negative serum pregnancy test performed within 7 days prior to the start of study drug. Post-menopausal women (defined as no menses for at least 1 year) and surgically sterilized women are not required to undergo a pregnancy test.
8. Subjects (men and women) of childbearing potential must agree to use adequate contraception beginning at the signing of the ICF until at least 2 months after the last dose of study drug. The definition of adequate contraception will be based on the judgment of the treating physician or a designated associate.  
**NOTE:** Examples of adequate contraception may include but are not limited to a combination of any two of the following:
  - Use of oral, injected or implanted hormonal methods of contraception
  - Placement of an intrauterine device (IUD) or intrauterine system (IUS)
  - Barrier methods of contraception: condom or occlusive cap (diaphragm or cervical/vault caps) with spermicidal foam/gel/film/cream/vaginal suppository
  - Total abstinence
  - Male/female sterilization
9. All subjects must have radiographically assessable disease per RECIST v1.1 obtained by imaging within 28 days prior to registration.
10. Must be able to swallow and retain oral medication.
11. Subject must be deemed a suitable candidate for regorafenib as per their treating physician

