18. Persistent proteinuria  $\geq$  Grade 3 NCI CTCAE v4.0 as defined as  $> 3.5$  g/24 hours, measured by urine protein: creatinine ratio on a random urine sample.
19. Interstitial lung disease with ongoing signs and symptoms at the time of study registration.
20. Pleural effusion or ascites that causes respiratory compromise ( $\geq$  NCI CTCAE version 4.0 Grade 2 dyspnea).
21. History of organ allograft (including corneal transplant).
22. Known or suspected allergy or hypersensitivity to any of the study drugs, study drug classes, or excipients of the formulations given during the course of this trial.
23. Any malabsorption condition which, in the opinion of the treating physician, will affect the absorption of any of the agents used in this study.
24. Women who are pregnant or breast-feeding.
25. Any condition, which, in the site investigator's opinion, makes the subject unsuitable for trial participation.
26. Substance abuse, medical, psychological, or social conditions that may interfere with the subject's participation in the study or evaluation of the study results.
27. Treatment with any investigational agent within 28 days prior to registration.

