#### **4. SUBJECT REGISTRATION**

All subjects must be registered and randomized through the Hoosier Cancer Research Network (HCRN) electronic data capture (EDC) system.

Subjects must be registered and randomized prior to starting protocol therapy. Subjects must begin therapy **within 5 business days** of randomization.

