**Footnotes:**

CBC=complete blood count; CT=computed tomography; D=days; ECOG=Eastern Cooperative Oncology Group; ICS = informed consent; MFSI-SF= Multidimensional Fatigue Symptom Inventory-Short Form

1. Serum chemistries (creatinine, glucose, total protein, blood urea nitrogen [BUN], total carbon dioxide [CO2], albumin, total bilirubin, alkaline phosphatase, and aspartate transaminase [AST] and alanine transaminase [ALT]) and electrolytes (total calcium, chloride, potassium, sodium)
2. All subjects will have PT/INR/aPTT at screening and End of Treatment Visit. ONLY subjects who are prophylactically treated with an agent such as warfarin or heparin must have close monitoring on Cycle 1 Day 5 and Day 1 of each cycle. If either of these values is above the therapeutic range, subjects should have at least weekly evaluations until INR/PTT is stable based on a measurement that is pre-dose as defined by the local standard of care.
3. Complete only for women of childbearing potential
4. Baseline CTs must be completed within 28 days prior to registration. CTs for re-staging will be performed after Cycle 2 (8 weeks) is complete and may be performed  $\pm$  5 days of scheduled clinic visit. Regardless of randomization, all subjects will follow up with their physician to discuss results.
5. Regorafenib 160 mg PO once daily will be administered for 3 weeks on/1 week off. If subject randomizes to receive Ginseng: 2,000 mg PO per day (1,000 mg BID), every day of each 28-day cycle. For subjects that randomize to ginseng, if regorafenib is held due to toxicity the ginseng may continue per protocol schedule.
6. See Study Procedures Manual for MFSI-SF and PROMIS questionnaires and additional information. The research nurse will provide the questionnaires to the subject as well as instructions on completion of the questionnaires. These instructions should include the importance of the subject completing the surveys without family assistance. The first set of surveys will be administered by the research nurse in the clinic via interview. The remainder of the surveys will be self-administered by the subject in clinic. If the subject has a question regarding the surveys the research nurse or physician will be available to respond. For pill count, please ask the subject to bring their pill bottle to verify number of doses taken at the time of clinic visit.

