### Within 7 days of study registration

- ECOG performance status
- Laboratory testing:
  - Complete Blood Count (CBC) with differential and platelet count
  - Complete metabolic profile (CMP) including: serum chemistries (creatinine, glucose, total protein, blood urea nitrogen [BUN], total carbon dioxide [CO2], albumin, total bilirubin, alkaline phosphatase, and aspartate transaminase [AST] and alanine transaminase [ALT]) and electrolytes (total calcium, chloride, potassium, sodium)
  - PT/INR and aPTT
  - Urine pregnancy test or serum HCG (only for women of child bearing potential)
  - Urinalysis should be done if proteinuria is suspected as per site investigator's discretion.

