## 7.2 On Treatment

### 7.2.1 Cycle 1 Day 1

**NOTE:** Cycle 1 Day 1 testing need not be repeated if completed within 7 days of starting protocol therapy.

- Complete physical examination
- Vital signs including BP, weight and ECOG performance status
- Adverse event and concomitant medication assessment
- MFSI-SF and PROMIS questionnaires
- Drug administration as outlined in Section 5 and Study Calendar

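### Section 7.1 accepts a urine pregnancy test timed to registration, while inclusion criterion 7 requires a serum test timed to first dose, and no test is scheduled at Cycle 1 Day 1

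*Combined protocol and SAP*

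**What the plan says.** **Eligibility.** Section 3.1, item 7, sets the rule: "Women of childbearing potential must have a negative serum pregnancy test performed within 7 days prior to the start of study drug". Item 7 of the synopsis criteria has the same sentence. The specimen is serum and the clock runs back from first dose.

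**Screening procedures.** Section 7.1 lists "Urine pregnancy test or serum HCG (only for women of child bearing potential") under the heading "Within 7 days of study registration". Either specimen is accepted, and the clock runs from registration.

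**Gap to first dose.** Section 4 requires therapy to start "within 5 business days" of randomization.

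**Cycle 1 Day 1.** The list in section 7.2.1 has no pregnancy test. Its opening note says "Cycle 1 Day 1 testing need not be repeated if completed within 7 days of starting protocol therapy".

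**Calendar.** The schedule of events in section 7 has one pregnancy-test entry, read as the 7-day screening column, and names no specimen. Footnote 3 says only "Complete only for women of childbearing potential".

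**Related safeguards.** Under section 3.1, item 8, subjects of childbearing potential "must agree to use adequate contraception beginning at the signing of the ICF". Section 3.2, item 24, excludes "Women who are pregnant or breast-feeding".

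**The concern.** Two parts of the protocol set different rules for the same test. The difference is in both specimen and timing, and in each case the procedure list is looser than the eligibility criterion it should carry out.

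The first-dose anchor in criterion 7 does not look like loose phrasing. Criterion 6, immediately before it, ties its laboratory window to registration. Criterion 7 uses a different and stricter reference point. Section 7.1 groups the pregnancy test with those laboratory tests and loses the distinction.

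This matters because it is the only pregnancy test scheduled before dosing. A woman can meet section 7.1 at registration, and nothing scheduled afterwards prompts a check before her first dose. Two things are at stake: eligibility deviations that clearer text would prevent, and weaker protection against fetal exposure to study drug. The protocol treats pregnancy as serious. It requires withdrawal and SAE reporting (section 6.3) and 24-hour reporting of an exposed pregnancy (section 10.2.4).

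**Working it through.** The plan gives no figure to reproduce, so the check is a comparison of texts followed by a calendar count.

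**1. Texts side by side**

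| Source | Specimen | 7-day window counted from |
|---|---|---|
| Section 3.1 item 7 and synopsis item 7 | Serum | First dose |
| Section 7.1 | Urine or serum | Registration |
| Section 7 calendar row | Not named | Not stated (7-day screening column) |
| Section 7 footnote 3 | Not named | Not stated |
| Section 7.2.1 list | No test listed | Not applicable |

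The note in section 7.2.1 waives repeats of Day 1 tests. No pregnancy test is on that list, so the note neither adds one nor triggers a repeat of an old one.

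**2. Specimen**

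No arithmetic is needed. A woman tested by urine alone satisfies section 7.1 and fails criterion 7.

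**3. Maximum test age at first dose**

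Inputs: up to 7 days from test to registration (section 7.1) and up to 5 business days from randomization to first dose (section 4). Assumptions: registration and randomization fall on the same day, and there is no public holiday.

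- Weekday randomization: 5 business days = 7 calendar days, so the maximum age is 7 + 7 = 14 days, against 7 allowed.
- Saturday randomization: the fifth business day is 6 calendar days later, so 7 + 6 = 13 days.
- Sunday randomization: 5 calendar days later, so 7 + 5 = 12 days.

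A holiday, or a gap between registration and randomization, would lengthen these.

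**4. Which permitted schedules exceed the limit**

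Assume further that test, registration and first dose all fall on weekdays. Let a = business days from test to registration and b = business days from registration to first dose. Each runs from 0 to 5, giving 6 × 6 = 36 combinations for any registration weekday. Since 5 business days is 7 calendar days, the limit is exceeded when a + b > 5.

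| a | Values of b that exceed the limit | Count |
|---|---|---|
| 0 | none | 0 |
| 1 | 5 | 1 |
| 2 | 4, 5 | 2 |
| 3 | 3 to 5 | 3 |
| 4 | 2 to 5 | 4 |
| 5 | 1 to 5 | 5 |

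The total is 1 + 2 + 3 + 4 + 5 = 15 of 36. In these the test is 8 to 14 days old at first dose, which is 1 to 7 days over. The other 36 − 15 = 21 comply. They include a test 7 days before registration with same-day dosing, and a test on the registration day with dosing 5 business days later.

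This counts what the text permits. It gives every schedule equal weight and does not forecast how often a breach would occur.

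**The case against.** The strongest reply is that criterion 7 is mandatory and governs enrolment. Section 7.1 does not say that a urine result satisfies it, serum is one of the two options listed there, and a serum test taken within 7 days before both registration and first dose meets every section. The calendar's 7-day column states no anchor and could be read as counting back from Day 1. On this view the defect is one loose line, and a careful site would not be caught by it. That both texts can be met together is correct. It limits the claim to what a site *can* miss, but it does not remove the conflict, because exact compliance with section 7.1 can still breach criterion 7.

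A second reply is that the consequences cannot be quantified. This stands. The documents give no number of women of childbearing potential among the 90 planned subjects and no comparison of urine and serum test performance. Contraception is required from consent, so it covers the interval between test and dose, and pregnancy is separately exclusionary. These measures reduce the residual risk, but neither schedules a test.

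A third reply concerns the remedy. A test at Cycle 1 Day 1 comes after randomization, so a positive result would arise in a randomized subject. Section 6.3 already covers that case by requiring withdrawal for pregnancy.

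**Conclusion.** The concern holds. The current text contains two incompatible rules for the pre-dose pregnancy test, and nothing in the calendar, its footnotes or the Cycle 1 Day 1 section reconciles them. Following section 7.1 can breach criterion 7 on specimen in any woman tested by urine alone. It can breach it on timing whenever the intervals from test to registration and from registration to dose together exceed 7 days.

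The 14-day figure is the worst case for weekday randomization with no holiday and same-day registration and randomization; it is not the typical case. The frequency of deviations and the added exposure risk cannot be estimated from the documents. Sample size, power and the primary analysis are not affected. The point should be corrected because it concerns patient safety and eligibility and is cheap to put right.

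**What to change.** Keep criterion 7 as the governing rule and bring the procedure text into line with it:

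- **Section 7.1:** replace the pregnancy-test line with one that requires serum, is limited to women of childbearing potential, and states its own window of 7 days before first dose. The window must be in the line itself, because the heading above it counts from registration.
- **Section 7.2.1 and the calendar's Cycle 1 Day 1 column:** add the serum test, with a negative result required before the first dose. The existing note then waives the repeat when the screening test is still within 7 days.
- **Calendar footnote 3:** add the specimen and the first-dose anchor.

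With these changes the oldest acceptable test at first dose is 7 days, down from a possible 14. The cost is wording in four places and at most one repeat blood test for a woman whose window has lapsed by first dose. Criterion 7 already implies that repeat.
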